CHAGNING HABITS AND LIFESTYLES IN OLDER INDIVIDUALS

Registration: NCT02777918

Date of Document: 26.07.2018

INCREASING EGG AND DIETARY PROTEIN INTAKE IN COMMUNITY-DWELLING OLDER ADULTS USING RECIPES AND SINGLE-USE HERB / SPICE PACKETS: A RANDOMIZED CONTROLLED TRIAL

METHODS

The study used a parallel group, randomized controlled intervention design, where community-dwelling older adults were randomized to receive or not receive high-protein egg-based recipes and herb/spice packets for 12 weeks, and egg intake, protein intake, and measures of health and well-being were measured at baseline, at the end of 12 weeks and after a further 12 weeks.

Participants

Older adults were considered for inclusion in the study if they were: 55 years and over; living in the community; not allergic to eggs; not knowingly suffering from hypercholesterolaemia or familial hypercholesterolaemia; not knowingly suffering from known renal insufficiency; not having undergone chemotherapy or radiotherapy in the last 6 months; not suffering from any condition, or receiving treatment that affected eating or sense of flavour; were able to give consent and complete all questionnaire measures; and did not have a pacemaker or defibrillator. These inclusion criteria allowed inclusion of volunteers within our target population (older adults living in the community), while ensuring against adverse health consequences as a result of a change in eggs or dietary protein consumption (British-Heart-Foundation, 2015; Pedrini, Levey, Lau, Chalmers, & Wang, 1996) or involvement in the study, and valid outcome assessments (Jacobsen et al., 1993; Steinbach et al., 2009; Van Cutsem & Arends, 2005).

Sample size:

Data from the National Diet and Nutrition Survey (NDNS) show that UK adults over 65 years old have a mean daily protein intake of 69.8g (SD = 20.3) (Bates et al., 2014). Assuming a threshold to stimulate muscle protein synthesis of 25-30g protein per meal (Paddon-Jones & Rasmussen, 2009) for three meals per day, daily intake should be at least 75-90g per day, an increase of on average 12.7g of protein per day. Assuming no change in the control group over the intervention period, and an alpha of 5% for a power of 0.8, the required sample size to detect a 12.7g increase in protein intake in the intervention group equals 41 participants per group. Taking into account a possible drop-out of 20%, we aimed to recruit 50 participants per study group.

Recruitment:

Participants were recruited via contact lists of individuals who have volunteered in previous studies; organisations that ran group meetings within the target population, e.g. bridge clubs; and by flyers and posters at local community buildings, such as museums and libraries. All volunteers were initially screened for suitability by telephone or email, and they were sent a participant information sheet before coming to the University for the baseline test session. Screening was repeated at this test session, and consent completed. Participants were not informed of the aim of the study, but were instead told the project was studying habits and lifestyles in older adults.

Randomisation:

All eligible volunteers were randomized into one of two groups: intervention and control, following consent. Randomisation was stratified per ten year age group (55-64, 65-74, 75-85, 85+) and by earlier involvement in related research [ref], using blocks of 6-10 participants, with an exception that couples were always allocated to the same group. Randomization was undertaken by a researcher with no direct contact with participants ([name]).

Intervention

Community-dwelling older adults randomized to the intervention group received six high-protein egg-based recipes and herb/spice packets every two weeks to their home address, for twelve weeks. Recipes were intended to provide ideas for consuming eggs in different ways and using different flavours, to increase variety in the overall diet. Each recipe contained one or two eggs, and provided 25-30g of protein per meal.

The 36 different recipes were gained from the website www.eggrecipes.co.uk, developed by the British Egg Industry Council (British-Egg-Industry-Council, 2016), selected as suitable for breakfast / brunch as well for other meals, and amended to contain 25-30g of protein. Participants in the intervention group received six sets of six recipes. Each set of recipes included a variety of egg preparations (e.g. fried eggs, scrambled eggs, omelettes); a variety of preparation times and methods (hob, oven, microwave); meat, fish and vegetarian dishes; and a variety of traditional (bacon, cheese, ham) and foreign flavours e.g. Indian, Turkish, Moroccan, Italian. Several of the recipes were developed by chefs known from UK television. Recipes were printed in large clear text on glossy A5 recipe cards, to aid durability and simulate supermarket recipe cards, and included preparation time and nutritional composition, with the protein content highlighted in bold. All recipes mentioned the dish was high in protein, and recommended consumption for breakfast or brunch. Recipe cards were pilot tested with individuals in the target age group, prior to use, and the text on several recipes was altered for face validity as a result. A list of all recipes can be found in Supplementary Materials I.

All herb/spices mentioned in the recipes were also provided for one preparation of the dish as part of the intervention. Herbs/spices were provided to reduce disuse of the recipes through ingredient expense. Other ingredients were not provided to result in an intervention that could be manageable in a real life scenario.

Control

Participants in the control group did not receive any recipes, herbs or spices, or the recipe feedback forms, but received all other documentation and undertook all tests sessions in the same manner as the intervention group.

Outcomes

Our primary outcomes were egg intake, protein intake (total), protein intake from animal-based foods and adverse events. Secondary outcomes were lean body mass and various functional measures of lean body mass. Variables of potential influence on these outcomes were also assessed, to include various demographic and lifestyle characteristics, energy intake, BMI, usual physical activity levels, health-related quality of life, reasons for eating / not eating eggs, and recipe feedback (intervention group only) Morton et al., 2017). Some of these additional variables were included in analyses to control for potential confounding, some were used only to describe the sample and some were used to investigate further any reasons for intervention success or failure.

Primary Outcomes:

Egg intake: Egg intake was measured using two measures: an egg consumption Food Frequency Questionnaire (FFQ) measure [ref] and the egg section of a validated FFQ [SCG-FFQ, Clark, 2017; Masson et al., 2003]. The egg consumption FFQ requested frequency of consumption of 18 preparations of egg: boiled eggs (hot), hard boiled eggs (cold), fried eggs, scrambled eggs, poached eggs, omelettes, scotch eggs, quiches/savoury flans, egg sandwiches, egg salad, custards, meringues, sweet flan/crème caramel, duck/quail's eggs, raw eggs, egg yolk separate from the white, and egg white separate from the yolk. For each type of egg, participants were asked to complete number of measures (e.g. 1 egg, 1 slice) consumed per day (1, 2, 3, 4, 5+) on number of days per week, using response options 1 - 7 days per week, once or twice per month, or rarely / never. Responses were converted to number of eggs eaten per month, where the category 'rarely or never' was counted as 0 times eaten per month, 'once or twice per month' as 1.5 times, and 1 to 7 days per week, as 4, 8, 12, 16, 20, 24, and 28 times per month, respectively. All foods were considered to contribute equal portions of eggs, excepting the egg dishes custards, meringues, and sweet flan / crème caramel, where each consumption was considered as 0.5 portions, because a standard portion tends to be less than one egg.

The SCG-FFQ is a validated FFQ, developed by the Scottish collaborative group, measuring dietary intake over the last two-three months (Clark, 2017; Masson et al., 2003). The section on egg intake consists of

three questions: number of measures (eggs) per day, and the number of days per week they eat 'Boiled or poached eggs'; 'Fried eggs'; and 'Scrambled eggs or omelette'. Response options were used and converted to monthly egg intake as above.

Protein intake: Protein intake was measured using the complete SCG-FFQ, where food intake data were converted to protein intake and protein intake from animal sources, by the Scottish collaborative group (Clark, 2017). Protein intake from animal sources consisted of protein intake from meat, fish, eggs, and dairy foods. Protein intake is known to be related to egg intake (Ruxton, Derbyshire, & Gibson, 2010, questionnaire study), to muscle mass, strength and function (Houston et al., 2008; Loenneke, Loprinzi, Murphy, & Phillips, 2016; Tieland et al., 2012), and to positive health outcomes in older adults (Hannan et al., 2000; Lord, Chaput, Aubertin-Leheudre, Labonté, & Dionne, 2007). Animal based proteins contain all essential amino acids and are considered high quality protein sources (van Vliet, Burd, & van Loon, 2015). Animal protein stimulates a higher net protein synthesis than a high plant protein diet (Pannemans, Wagenmakers, Westerterp, Schaafsma, & Halliday, 1998). These measures also allowed investigation of any replacement of other high protein foods by egg based protein foods.

Adverse events: To assess adverse events, participants were asked whether during the previous month they had experienced any of the following effects more or less often than usual: nausea, digestive issues (e.g. constipation or diarrhoea), stomach aches/cramps, hunger, bloating/uncomfortable fullness, thirst, headaches, fatigue/tiredness, restlessness, dizziness, or skin rashes. If they answered yes to any of these questions, they were asked if they knew of any reason for this, or they had experienced anything else that was different than usual.

Secondary Outcomes:

Lean Body Mass: Fasting resting body composition was assessed by bioelectrical impedance analysis (BIA) with the use of a 50-kHz generator (1500 MDD; Bodystat, Isle of Man, UK). Under standard conditions, BIA measures are validated against MRI measures of skeletal muscle mass (Janssen, 2002; Janssen et al., 2000). The equations have been validated for adults of multiple ethnicities (Janssen et al., 2000), and have been established and recommended for older adults (Cruz-Jentoft et al., 2010; Kyle, Genton, Slosman, & Pichard, 2001; Roubenoff et al., 1997). Assessments were conducted after an overnight fast, following no alcohol or caffeine for 12 hours prior to the measurement. Water consumption, exercise and use of sauna during eight hours prior to the session were recorded and kept constant across sessions.

Functional measures of lean body mass: Physical performance was assessed using a short physical performance battery (SPPB) (Guralnik et al., 1994), consisting of three physical functioning tests measuring: lower body strength (chair stands), standing balance, and walking speed (8-foot walk). For the chair stands, participants were asked to stand up from a chair and sit down five times with their arms across the chest and time is measured. For the balance test, participants were instructed to stand in different positions: side-by-side, semi-tandem, and full-tandem position, while being timed for 10 seconds, or until they lost their balance. Walking was measured by asking the participant to walk an 8-foot walking course, at their usual speed, as if they were walking down the street to go to the shops. Times were recorded twice, and the fastest used for analyses. Scores from zero to four are derived for each of the three components and totalled following the instructions by Guralnik et al. (Guralnik et al., 1994). Total SPPB scores range from 0 to 12 with a higher score indicating better physical performance. The measures are relatively quick, include activities that are used in everyday life, and are non-invasive for the participants. SPPB measures have been linked to self-reported disability, predict mortality and nursing home admission (Guralnik et al., 1994), and have been recommended for measuring physical performance in frail old people (Cruz-Jentoft et al., 2010). Statistically significant improvements in SPPB scores have been found in older adults following increased protein intake (Tieland et al., 2012) and the method can measure clinically meaningful changes (Kwon et al., 2009).

Leg strength was measured in a seated position by counting number of times participants could extend their leg wearing ankle weights (of 5kg, 2.5kg, or no weights) during a set amount of time (one minute or 30 seconds). Ankle weight and time was chosen by the researcher during the first test session based on estimated ability of the participant after the participants had performed the other exercises, and held constant for all other test sessions. The 2.5kg weights and one minute duration were chosen for most participants. Handgrip strength was also measured using a hand grip dynamometer (Takei, GRIP-D, T.K.K. 5401) (Watanabe et al., 2005). Participants were asked to take three measures of handgrip strength for each hand, alternating between right and left hands, while standing up (or sitting if standing was not possible). The maximum of the six measures was reported (Roberts et al., 2011). Handgrip strength and leg extension are commonly used non-invasive measures to assess muscle function in older adults (Beasley, Shikany, & Thomson, 2013), and only take a few minutes. These measures have been associated with health related quality of life (Sayer et al., 2006), nutritional status (Norman, Stobäus, Gonzalez, Schulzke, & Pirlich, 2011), and future physical performance and disability (Rantanen et al., 1999). Handgrip strength also relates strongly to lower extremity muscle power and mobility (Lauretani et al., 2003), and has been recommended for a quick and inexpensive sarcopenia screening tool (Lauretani et al., 2003). Sarcopenia cut off points per gender based on measured handgrip strength were used to estimate sarcopenia prevalence (Cruz-Jentoft et al., 2010; Lauretani et al., 2003; Murphy et al., 2017).

Additional Outcomes:

Demographic and lifestyle characteristics: Assessed demographic and lifestyle characteristics were: date of birth; gender; marital status (married, divorced, widowed, never married); living status (alone, with others); years of education; nationality; most recent level of employment (unemployed, manual worker, non-manual worker, professional / management); frequency of help with food shopping or preparation, eating out or away from the home, and of food delivery (never, sometimes, often), vegetarianism, pescatarianism or veganism (yes or no), and denture wearing (no, partial dentures or full dentures). All variables have previously been shown to be related to eating behaviour in older adults and protein intake specifically (Appleton, 2016; Best & Appleton, 2013; Kremer, Bult, Mojet, & Kroeze, 2007; Steptoe, Pollard, & Wardle, 1995) (Adams et al., 2015; Caraher, Dixon, Lang, & Carr-Hill, 1999). Food neophobia - a measure of willingness to try new foods, was also assessed using a validated questionnaire (Pliner & Hobden, 1992), as increases with age may pose a barrier to trying the recipes in the intervention (Meiselman, King, & Gillette, 2010; Tuorila, Lähteenmäki, Pohjalainen, & Lotti, 2001). Additionally, a validated questionnaire was used to assess symptoms of sarcopenia (Malmstrom & Morley, 2013).

Energy Intake: Energy Intake was assessed as part of the SCG-FFQ, by consideration of all foods, by the Scottish collaborative group (Clark, 2017).

BMI: Body Mass Index was calculated from measured standing height and body weight (in light clothing, without shoes), measured to the nearest 0.1cm and 0.1kg, using a stadiometer (SECA gmbh & co, Hamburg, Germany) and calibrated scale (The Boots Company PLC, Nottingham, UK) respectively.

Usual Physical Activity: Physical activity, as energy expended in physical activity per week, was assessed using the Community Healthy Activities Model Program for Seniors (CHAMPS), a physical activity questionnaire for older adults (Stewart et al., 2001). The CHAMPS lists a variety of light, moderate and vigorous physical activities, and requests weekly frequency of performing each activity in number of hours per week (response options: less than 1 hour, 1-2.5 hours, 3-4.5 hours, 5-6.5 hours, 7-8.5 hours, and 9 or more hours). Responses were converted to four outcomes (Stewart et al., 2001), and estimated caloric expenditure per week on all activities was used for analyses. Physical activity is strongly related to muscle mass and strength (Cruz-Jentoft et al., 2010; Goodpaster et al., 2008), and a recent review showed that experience in exercise made protein supplementation with resistance training more effective (Morton et al., 2017). Studies also show associations between higher egg intake and low physical activity (Hu et al., 1999).

Health related quality of life: Health related quality of life (HR QoL) was assessed using the short form-36 questionnaire (SF-36) (Ware Jr & Sherbourne, 1992). Scores for all nine domains were generated (Ware Jr & Sherbourne, 1992) and added up to give a total SF-36 score, where a higher score suggests a greater HR QoL. SF-36 scores have been associated with muscle strength and physical performance (Syddall, Martin, Harwood, Cooper, & Sayer, 2009).

Reasons for eating or not eating eggs: Reasons for eating / not eating eggs were assessed by questionnaire, as previously developed [ref], to give insights into other possible barriers to trying the recipes.

Recipe feedback: Intervention group participants also received a recipe feedback form in the post after the 12 week intervention and after the following 12 weeks. This form asked for comments on which recipes and herb/spice packets they used or did not use, and why. Recipe feedback forms were sent by post after the test sessions, so that the completion of these does not impact on our primary outcomes, by a researcher unassociated with testing to maintain blinding.

Procedure

A schematic overview of the study design can be found in Figure 1. All participants came to Bournemouth University for a test session at baseline (T1), after 12 weeks intervention (T2), and after a further 12 weeks (T3). A week before each test session, participants received a set of questionnaires by post, to complete and bring to the test session. Queries were discussed at the test session, but on a few occasions, participants finished the questionnaires at home within a few days after the test session, and returned them by post. All test sessions were conducted in the morning between 8.00 and 11.00, at a time of the participant's preference. Participants came fasted, and were asked to have had only water to drink since going to sleep the night before the test session. Height and weight were measured first, followed by bioelectrical impedance measures of body composition. After these measures, a breakfast of toast / cereal and coffee / tea was provided. While the participant was eating breakfast, questionnaires were checked for missing values and any queries were discussed. After breakfast, the functional measures of lean muscle mass were undertaken. Questionnaires and tests undertaken were the same for each test session (T1, T2, T3), excepting that demographic and lifestyle characteristics, and reasons for eating / not eating eggs were only assessed at baseline. Test sessions were individual, or if preferred per couple, and lasted approximately an hour per person. After the baseline test session, all participants also received a postcard with a short dietary information message, including the importance of dietary protein for older adults and why it may be beneficial to eat more protein, and to do so for breakfast. This was included to add relevance to the recipes for those in the intervention group, but made no reference to the recipes or intervention, but was identical for all participants.

Blinding:

Outcome assessments were undertaken by a researcher who was blind to intervention group ([name]). Recipes and herb/spice packets were sent to intervention participants by a researcher with no direct contact with participants ([name]). Participants were not blind, although they were blind to the other possible conditions, thus the control group did not know about the intervention, nor the details of the intervention. Participants in the intervention group were asked not to mention the recipes to researchers.

Ethical Approval and Trial Registration

Ethical approval for this study was granted by the Research Ethics Committee of Bournemouth University, prior to commencement. Participant recruitment started in May 2016, and test sessions were run from June 2016 to April 2017. The study was registered at ClinicalTrials.gov in May 2016 (NCT02777918).

Data analyses

Data were analysed using IBM SPSS Statistics for Windows, version 22, using an Intention-to-treat approach. First, all measures were tested for normality. All baseline measures were then compared

between the intervention and control group using χ^2 tests and Mann-Whitney U tests. Demographic and lifestyle characteristics were used to describe the sample. Correlations were investigated between all baseline measures. Multiple linear regression analyses were then used for the main analyses (Vickers & Altman, 2001). The effect of the intervention on all outcome measures was assessed using multiple linear regression, controlling for age, gender, baseline measures of the dependent variable, previous participation in related studies, and measures of total protein intake, BMI, usual physical activity and HR QoL score as assessed at the same time. Previous participation was included in regression models to allow for possible demand characteristics. Energy intake was not included in regression models following high correlations with BMI. Other demographic and lifestyle characteristics were also not included to maintain statistical power (Howell, 2012]. Separate regression models were used to predict egg intake, total protein intake, protein intake from animal sources, adverse events, lean body mass, physical performance, handgrip strength, and leg extensions as the dependent variables. Similar analyses were conducted once at the end of the 12 week intervention (T2) and once at the end of the following 12 weeks (T3). Egg intakes from the two different measures were compared using correlations and multiple linear regressions were conducted for both measures. Reasons for eating / not eating eggs and details on recipe feedback will be analysed further at a later date. These data and some of the data of participant demographic and lifestyle characteristics will be published elsewhere in exploratory analyses investigating intervention success / failure. Missing data were completed using last observation carried forward. Data are reported using means and standard deviations.

Figure 1: Schematic overview of the study design

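### Does the protein postcard sent to controls undo the sample size's assumption of no change in the control group?

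*Combined protocol and SAP*

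**What the plan says.** All references are to the combined protocol and SAP.

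- **Sample size.** Survey intake in UK adults over 65 is 69.8 g/day (SD 20.3). The target comes from a per-meal threshold over three meals: "daily intake should be at least 75-90g per day, an increase of on average 12.7g of protein per day". The premise is "Assuming no change in the control group over the intervention period, and an alpha of 5% for a power of 0.8", and the result is that "the required sample size to detect a 12.7g increase in protein intake in the intervention group equals 41 participants per group". Allowing for 20% dropout, the aim was 50 per group.
- **Control.** Controls got no recipes, herbs, spices or recipe feedback forms, but "received all other documentation and undertook all tests sessions in the same manner as the intervention group".
- **Procedure.** After baseline, "all participants also received a postcard with a short dietary information message, including the importance of dietary protein for older adults". The card also gave reasons for raising protein intake, at breakfast in particular. It "made no reference to the recipes or intervention, but was identical for all participants". The section gives the reason: to make the recipes relevant to those who would receive them.
- **Data analyses.** "The effect of the intervention on all outcome measures was assessed using multiple linear regression", with the baseline value of the outcome among the covariates. The approach is intention-to-treat, missing data are filled by last observation carried forward, and results are reported as means and SDs.

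**The concern.** The 12.7 g/day is a need: the distance from average intake to the middle of the target range. The plan places it in the intervention group as that group's whole rise, whereas the regression tests the difference between groups. The two are the same quantity only if controls stay where they were, and controls were sent a message that encourages a rise in the very outcome the trial is sized on.

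If both groups rose, the intervention group could gain its full 12.7 g/day while the tested difference fell short of it. Power would then be below the stated 0.8, and a non-significant group effect might be misread as a failure to raise intake. Total protein intake is a primary outcome, so the question deserves a check.

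**Working it through.** **Inputs from the documents.** Mean 69.8 g/day, SD 20.3, target 75-90 g/day, alpha 5%, power 0.8, dropout 20%, 50 recruited per group. Sidedness is not stated; two-sided reproduces the plan's figure, while one-sided gives 32 per group.

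**Assumed inputs.** The control rise (0 to 5 g/day) and the correlation r between baseline and follow-up intake (0.3 to 0.7). The documents give neither.

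**1. Reproduce the plan.** Effect: (75 + 90)/2 − 69.8 = 82.5 − 69.8 = 12.7 g/day. Normal approximation: n = 2 × [20.3 × (1.960 + 0.842)/12.7]² = 40.1, so 41 per group. This matches. Inflation: 41 × 1.2 = 49.2, so 50. With 20% lost, 50 × 0.8 = 40 complete.

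**2. Slack.** The smallest difference detectable with 80% power at 41 per group is 20.3 × √(2/41) × 2.802 = 12.6 g/day, against 12.7 assumed.

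**3. Power if controls rise by x.** The tested difference is 12.7 − x. Two-sided 5%, noncentral t, 40 per group; the adjusted SD is 20.3 × √(1 − r²).

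| Control rise x (g/day) | Unadjusted | r = 0.3 | r = 0.5 | r = 0.7 |
|---|---|---|---|---|
| 0 | 0.79 | 0.83 | 0.89 | 0.97 |
| 1 | 0.72 | 0.76 | 0.84 | 0.95 |
| 3 | 0.56 | 0.60 | 0.68 | 0.84 |
| 5 | 0.39 | 0.42 | 0.49 | 0.65 |

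Detectable differences at 80% power are 12.28, 11.15 and 9.20 g/day for r = 0.3, 0.5 and 0.7. Adjusted power therefore drops below 0.80 once controls rise by 12.7 − 12.28 = 0.42, 12.7 − 11.15 = 1.55 or 12.7 − 9.20 = 3.50 g/day.

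**4. Does the table describe the planned analysis?** Not closely. It drops the 20% who leave. The plan keeps them, with their last value carried forward, so about 50 per group are analysed if recruitment is met.

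- 50 per group, no dilution, unadjusted: power 0.87, 0.81 and 0.66 for control rises of 0, 1 and 3 g/day.
- 50 per group, no control rise, 20% of the intervention group carrying a baseline value forward: the difference becomes 0.8 × 12.7 = 10.2 g/day, and unadjusted power is 0.70.

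The choice of model for dropout alone moves power between 0.70 and 0.87 with no control rise at all.

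**5. What a non-significant result could say.** With 40 per group and SD 20.3, the unadjusted 95% CI half-width is 1.99 × 20.3 × √(2/40) = 9.0 g/day (6.5 at r = 0.7). An observed difference of 8 g/day would be non-significant unadjusted, with limits of about −1 and 17 g/day. The upper limit lies above 12.7. Such a result is inconclusive; it would not show that recipes added little to the message.

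**6. Would within-group intervals help?** For 40 per group, the SD of change is 20.3 × √(2(1 − r)) = 24.0, 20.3 and 15.7 for r = 0.3, 0.5 and 0.7, giving 95% half-widths of 7.7, 6.5 and 5.0 g/day. A rise of 12.7 g/day would be visible. It would still be an uncontrolled change over time, which season, repeated questionnaires or the postcard could each explain.

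**The case for a change.** The strongest case for a change is that the plan's own text pulls two ways: it assumes that controls stand still, then sends them a prompt to eat more protein. The shared postcard cancels out only if recipes add 12.7 g/day on top of it, and the Sample size section does not claim that; it makes 12.7 the intervention group's entire rise. On that reading any control rise is subtracted, and a rise of at most 3.5 g/day, 5.0% of the survey mean (3.5/69.8), takes adjusted power below 0.80 across the assumed range of r. SDs at each visit do not yield a confidence interval for change, and the plan names neither an analysis of change within groups nor a comparison with 75-90 g/day. The remedy would cost only a few extra estimates and some wording.

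The tension and the power figures stand, as conditional statements. The remedy is where the case weakens:

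- A note that 12.7 depends on controls not changing repeats a condition the section already states.
- Defining the estimate as recipes and packets added to the message repeats what the design description, Control and Procedure sections already make plain.
- Within-group intervals limited to people with both measurements would leave the stated intention-to-treat approach and alter no result. Setting daily means against 75-90 g cannot show that the per-meal threshold was met.
- A rule that reads a non-significant difference, with both groups rising, as recipes having added little would be wrong, as step 5 shows.

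**Conclusion.** No change to the plan is called for. The 41 per group is correct for a between-group difference of 12.7 g/day under a condition the plan states. That condition is uncertain because of the postcard, and the cost of its failing is real but unknown: unadjusted power of 0.72 to 0.39 for assumed control rises of 1 to 5 g/day with 40 per group, and less loss with a strong baseline correlation (0.95 to 0.65 at r = 0.7). Nothing in the documents shows that any control rise occurred. At 40 completers, the gap between 0.80 and 0.79 with no control rise is rounding.

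Giving both arms the same message is a fair trade-off. It makes the recipes relevant without favouring one group, and the comparison remains a valid contrast for recipes and packets on top of that message. An analyst following the plan reports group means and SDs, can see from them whether both groups rose, and should read a non-significant effect from its confidence interval. Testing ended in April 2017 and the document is dated July 2018, so no recalculation could alter recruitment.

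This conclusion covers the postcard and the no-change assumption only. It rests on the survey SD applying to this sample and on the assumed ranges for r and the control rise; the power figures credit adjustment for baseline alone, not for the other covariates in the model.

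### The target of 50 per group leaves 40 after the plan's own 20% drop-out, one short of the 41 it says it needs; the loss of power is about one percentage point or less

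*Combined protocol and SAP*

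**What the plan says.** The Sample size section (under Methods, Participants) takes a survey mean protein intake of 69.8 g/day with SD 20.3, and sets the target at "an increase of on average 12.7g of protein per day". The calculation is made "Assuming no change in the control group over the intervention period", with "an alpha of 5% for a power of 0.8". The resulting requirement "equals 41 participants per group". The next sentence allows for possible drop-out of 20% and ends with "we aimed to recruit 50 participants per study group".

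The section does not say whether the test is one- or two-sided, and it gives no formula for the drop-out allowance. The Data analyses section specifies an intention-to-treat approach, regression adjusted for the baseline value of the outcome among other covariates, and last observation carried forward for missing data.

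**The concern.** A drop-out allowance exists so that the required number remains after the assumed losses. Here the required number, the assumed loss and the recruitment target stand in adjacent sentences, and the third does not follow from the first two. The recruitment target is the only part of the calculation that the trial acted on, and this section is its stated justification. A reader will take it that 80% power was protected against 20% loss. On the plan's own figures it was protected against 18% loss. At stake is whether the stated power and the stated target agree, not whether the trial was viable.

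**Working it through.** **Inputs, all from the Sample size section.** Mean 69.8 g/day; SD 20.3 g/day; target intake 75 to 90 g/day; no change in controls; alpha 0.05; power 0.80; drop-out 20%; 50 recruited per group. Two-sided testing is an assumption. It is the reading that reproduces the plan's figure; a one-sided calculation gives 32 per group.

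**Step 1: the difference.** (75 + 90)/2 − 69.8 = 82.5 − 69.8 = 12.7 g/day, as stated.

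**Step 2: the plan's 41.** Normal approximation for two means:

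n = 2 × [(1.960 + 0.842) × 20.3/12.7]² = 40.11, rounded up to 41 per group. The stated figure is reproduced exactly.

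**Step 3: the drop-out allowance.**

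- Remaining from 50 at 20% loss: 50 × 0.80 = 40, which is below 41.
- Needed to keep 41: 41/(1 − 0.20) = 51.25, so 52 per group (104 in total, against 100).
- Largest loss at which 50 still leaves 41: 1 − 41/50 = 18%.

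**Step 4: what the missing participant costs.** Unadjusted two-sided power for 12.7 g with SD 20.3:

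| Remaining per group | Normal approximation | t-test |
|---|---|---|
| 40 | 79.9% | 78.9% |
| 41 | 80.9% | 79.9% |

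By either method, going from 41 to 40 costs about one percentage point. By the plan's own method, 40 falls 0.1 of a point below 80%. With 40 per group, the difference detectable with 80% t-test power is about 12.9 g (12.88), against the planned 12.7 g.

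**Step 5: where 50 could have come from.** Several routes end at 50:

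- 41 × 1.20 = 49.2, rounded up;
- the unrounded requirement, 40.11/0.80 = 50.13, rounded to the nearest whole number;
- 51.25 set to a convenient round target.

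The document does not distinguish between them.

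**The case against.** The strongest reply is that this is rounding. The unrounded requirement is 40.11, so 40 completers are about a tenth of a participant short, and power by the plan's own method is 79.9%. The 12.7 g is itself the midpoint of a range running from 75 − 69.8 = 5.2 g to 90 − 69.8 = 20.2 g, so a shift of about 0.2 g in the detectable difference changes no decision. This stands as to size. It does not remove the inconsistency: the plan rounded 40.11 up and stated 41 as its requirement, and 50 does not keep 41 at 20% loss by any route.

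A second reply is that the analysis is intention-to-treat with last observation carried forward, so it is not confined to 40 completers. That is true of the nominal number analysed, but it does not rescue the calculation. The plan itself inflates for drop-out, so it treats lost participants as needing replacement. Outcomes are measured only at baseline, 12 weeks and 24 weeks, so anyone lost before the 12-week visit carries forward a baseline value, that is, no change. As an illustration, assume that all 20% are lost before that visit and that completers gain the full 12.7 g. The expected difference is then 0.80 × 12.7 = 10.16 g, and t-test power with 50 per group and SD 20.3 is about 70%. If losses occur only after 12 weeks, the 12-week analysis is untouched. The documents do not give the timing, so this shows only that carrying values forward cannot be assumed to make up the shortfall.

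A third reply is that the main model adjusts for baseline, while the calculation uses the unadjusted SD. The documents give no baseline-to-follow-up correlation. If one assumes 0.17 and considers baseline adjustment alone, residual SD is 20.3 × √(1 − 0.17²) and t-test power at 40 per group is 80.1%; at 0.5 it is 89.1%. A weak correlation would cover the gap. This stands, and it is why the point is limited to the agreement of the stated figures.

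Finally, testing ended in April 2017, so the target cannot now change. That limits the remedy to the text.

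**Conclusion.** The inconsistency is real and minor. On the plan's own inputs, 50 per group leaves 40 at 20% loss against a stated need of 41. The gap is one completer, or two recruits, per group, and about one percentage point of power or less. The power figures assume a two-sided, unadjusted comparison with SD 20.3 in both groups and 20% loss in each.

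Three stronger readings are tempting, and the documents support none of them.

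- A reader might infer that the authors multiplied by 1.2 instead of dividing by 0.8. That fits the number, but so do the other routes in the working, and no formula is given.
- A reader might infer that the trial did not deliver 80% power. The completers-only, unadjusted calculation is not the planned analysis, and the planned analysis could have more or less power than 79–80%.
- A reader might infer that 41 is itself wrong, because a t-test needs 42, which inflates to 53. The normal approximation is a conventional choice and reproduces 41 exactly. The t-test figures rest on a different method and are not a correction to the plan's arithmetic.

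**What to change.** Restate the drop-out sentence in one of two ways:

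- say that 50 per group with 20% drop-out leaves 40 per group, giving about 79–80% power for a difference of 12.7 g/day (80% t-test power for about 12.9 g/day); or
- say that keeping 41 per group at 20% loss would have needed 41/0.80, that is 52 per group, and that 50 were sought.

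Either version should state the inflation formula and that the test is two-sided, if that was the intention. The cost is one sentence and a stated power that is very slightly less favourable. No extra enrolment and no change to the analysis are needed.
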